To assess group differences in the number of weeks of abstinence in the follow-up period (Aim-2a), a Poisson regression model was fit with the total number of weeks of self-reported abstinence in the four-week follow-up period as the dependent variable and treatment, site, and treatment by site interaction as independent variables. We conservatively imputed missing values as non-abstinent, thereby including the total ITT sample. We additionally performed a sensitivity analysis for weeks of abstinence by including the weeks preceding the 9th rTMS-treatment visit and immediate post-visit since these two weeks represent the time following the delivery of a total of 16-sessions of rTMS (a similar dose to early rTMS for depression studies). We calculated the relative risk of having a week of abstinence as a measure of the effect size, along with 95% confidence intervals. We used creatinine-corrected urine cannabinoids to verify self-reported abstinence at follow-up weeks 2 and 4, and calculated the proportion that these two methods were concordant.

To evaluate group differences in the number of days of cannabis use (Aim-2b), we utilized a GLMM with the number of days-per-week of cannabis use as the dependent measure. We included participants in the model who had follow-up data (the completer sample; N=51) and given the apparent divergence in days-per-week of cannabis use in the final two-weeks of the follow-up period, we chose to focus our analysis on that period.

Residual normality was assessed for each of the above models using QQ-plots. We included sex in all models to detect a potential effect, but when no significant effects were found, we excluded sex from the subsequent final models. Apart from craving, this was a pilot trial and not powered a priori to detect statistically significant differences; however, statistically significant *p*-values are noted when observed. When reported, a level of $\alpha = 0.05$ was used (two-tailed), and no adjustments for multiple comparisons were made for this preliminary investigation. Effect sizes at each time point were estimated as Cohens d using means and pooled standard deviations. Statistical analyses were conducted using R software (version 4.2.1, GNU project) and SAS version 9.4 (Cary, NC).

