To date there has been limited work examining the effect of rTMS on aspects of CUD. Drawing from the published literature suggesting that excitatory rTMS applied to the DLPFC can reduce craving, the candidate and mentorship team recently completed a preliminary sham-controlled crossover study in cannabis use disordered individuals. The trial suggested that rTMS is safe and well-tolerated, and that a single session of rTMS *acutely* decreases cannabis cue-induced craving. The promising results from our single session trial parallel the single session results found in nicotine and cocaine use disordered populations which subsequently translated into positive multiple session clinical trials(8, 9). As such, it follows that a trial utilizing multiple sessions of rTMS in cannabis use disordered patients may yield positive results.

The overarching goal of this proposal is to investigate if a course of excitatory DLPFC rTMS results in reduced cannabis cue-induced craving in treatment seeking individuals with CUD (Aim1). Additionally, we seek to explore the mechanistic underpinnings of any observed effect by collecting functional magnetic resonance imaging (fMRI) data during cannabis cue-administration before and after the treatment course (Aim 2). These aims will be addressed through a double-blind, randomized, sham-controlled study in which 72 treatment seeking cannabis use disordered participants (36/group) will be given 20 sessions of either *Active* or *Sham* excitatory rTMS applied to the DLPFC. rTMS will be delivered in an accelerated fashion as quickly as in two-weeks, but most often over five-weeks (2 sessions each day, 10 treatment-days). rTMS will be applied in conjunction with a validated three-session Motivational Enhancement Therapy (MET) behavioral intervention.

Aim 1: Determine if a course of excitatory rTMS applied to the DLPFC results in reduced cue-induced craving. We hypothesize that as compared to participants receiving sham rTMS, participants receiving active rTMS will have a reduced level of cannabis cue-induced craving following their final rTMS session as compared to prior to their first rTMS session. We will measure self-reported cannabis craving during a validated cannabis cue-reactivity paradigm, and define cue-induced craving as change in self-reported craving from pre-to-post cue administration.

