Sample Size Justification: The primary focus of this study is to show evidence, with sufficient strength, that treatment with active rTMS will result in decreased cue induced craving (Aim 1), and decreased BOLD response in reward network structures during a cue-reactivity fMRI paradigm (Aim 2) in CUD participants treated with either active or sham rTMS. For Aim 1: Within subject craving measures tend to be highly correlated when measured closely in time and thus we assume a conservative ICC of $p=0.75$ (previous CUD studies range $p=0.60-0.75$) with a standard deviation of ≈ 12.2 . We intend to detect a clinically meaningful craving score difference between the two treatment groups of 8.5 (Cohen's $d=8.5/12.2\approx 0.7$). This is a conservative estimate given that recent multi-session rTMS treatment trials have yielded larger effect sizes on craving ($d=0.98$ (7) in alcohol users, and $d=0.84$ (9) in cocaine users). In the proposed study we will measure increased craving (via MCQ total score) following the presentation of a validated cannabis cue paradigm both before and after a treatment course of rTMS. Under the assumption of independent observations, a total sample size of 32 participants equally allocated to each treatment assignments will provide 80% power with a type 1 error rate of 5% to detect the stated effect size of 0.7. However, the effective sample size in a repeated measures data setting is reduced when assuming an ICC of 0.75. The number of participants per group required is therefore estimated to be $n=27$. Additionally, we need to adjust for study attrition between randomization and the 4-week follow up visit. Assuming an attrition rate of up to 25%, a sample size of **36 participants randomized to each treatment group (n=72 total)** will provide adequate power to detect the primary aim effect size of $d=0.7$ between those receiving active and sham rTMS. **For Aim 2:** In a within subjects investigation of nicotine use disordered participants undergoing a single session of rTMS, there was a significant effect on BOLD response to smoking cues (see figure 2, Preliminary Studies section). If we assume that, as with previous study of cue induced BOLD reactivity in smokers using rTMS, our effects are of medium to large size (e.g. $d=0.7-0.8$) with alpha =5% (2-tailed), a sample of **36 randomized participants in each group will result in greater than 80% power for detecting effects of treatment on CR-BOLD response**. In sum, we are confident that the proposed randomized sample size of 72 participants will be sufficient to test Aims 1 and 2. **For our exploratory Aim**, our recent, non-contingency management based medication trials for cannabis cessation have shown varying placebo abstinence rates (defined as ≤ 50 ng/ml THCCOOH UCT) at the end of study (EOS) treatment (5-15%) (38, 39, 41). Since we are only hoping to provide preliminary data to power a more definitive study, our sample is not designed to sufficiently answer this question definitively. Despite this fact we will still have power to detect a large effect on abstinence. An rTMS abstinence rate of at least 30% greater than placebo at the end of study treatment under the most conservative conditions, at a 10% placebo abstinence rate, a randomized sample size of 36 participants in each treatment group will provide 80% power with a type 1 error of 5% to detect this difference at the end of this pilot study.

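### Aim 1 sample size: 27 per group at ICC 0.75 fits an average of repeated scores, but the hypothesis is a change, for which 0.75 is the favourable end of the quoted range

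*Combined protocol and SAP*

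**What the plan says.** The Aim 1 part of the protocol's Sample Size Justification begins with the correlation: "Within subject craving measures tend to be highly correlated when measured closely in time and thus we assume a conservative ICC of" 0.75, set against a range of 0.60-0.75 in earlier studies. Its other inputs are "with a standard deviation of ≈ 12.2" and a "clinically meaningful craving score difference between the two treatment groups of 8.5", which it converts to d of about 0.7. It gives 32 participants as a total under independence, which "will provide 80% power with a type 1 error rate of 5% to detect the stated effect size of 0.7". It then says that "the effective sample size in a repeated measures data setting is reduced when assuming an ICC of 0.75", and states 27 per group. Allowing for 25% attrition gives 36 randomised per group, 72 in all. It does not say whether 12.2 and 8.5 refer to one MCQ score, to a cue-induced change, or to a before-after change.

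Specific Aims, Aim 1, says the investigators will "define cue-induced craving as change in self-reported craving from pre-to-post cue administration". The hypothesis compares this after the final rTMS session with before the first, active against sham. The schedule of assessments also lists the primary outcome as a change in MCQ during the cue paradigm. The protocol and the SAP both plan mixed models with a treatment-by-time term; the SAP's dependent measure is the total MCQ-SF score. The Aim 1 sizing text gives no sidedness, but the SAP says its alpha of 0.05 "was used (two-tailed), and no adjustments for multiple comparisons were made".

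**The concern.** The ICC acts in opposite directions on an average and on a change. Averaging a subject's scores gains less when they are highly correlated, so a high ICC is cautious. Subtracting one score from another removes more noise when they are highly correlated, so a high ICC is favourable. The plan sizes Aim 1 with a figure that behaves like an average and labels the high ICC conservative, while the hypothesis is a change.

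The SAP names craving as the only outcome the trial was powered for. A null craving result would therefore be read against this power statement, so it should refer to the contrast that is tested.

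**Working it through.** **Inputs.** Difference 8.5, SD 12.2, ICC 0.75 (range 0.60-0.75), 80% power, 5% alpha and 25% attrition come from the Sample Size Justification. Two-sided testing comes from the SAP.

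**Step 1: the 32.** Per arm, n = 2(1.960 + 0.842)²/d². With d = 0.7 this is 32.04. So 32 is the per-arm size by the normal approximation, with power just under 80% (79.96%). Read as a total, 16 per arm has about 48% power by t-test with one observation each. A total of 32 would fit if each of 16 per arm gave two independent observations, but the text does not say this.

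**Step 2: the 27.** Each candidate multiplies 32 by a variance factor at ICC 0.75.

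| Quantity analysed | Factor | Result |
|---|---|---|
| Average of m = 2 scores | (1 + 0.75)/2 = 0.875 | 28.0 |
| Average of m = 3 | (1 + 2 × 0.75)/3 = 0.833 | 26.7, i.e. 27 |
| Average of m = 4 | (1 + 3 × 0.75)/4 = 0.8125 | 26.0 (26.03 from 32.04, rounded up to 27) |
| Before-after change in one score | 2(1 − 0.75) = 0.50 | 16.0 |
| Baseline-adjusted score | 1 − 0.75² = 0.4375 | 14.0 |
| Change in cue-induced change | 4(1 − 0.75) = 1.00 | 32.0 |

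Only the average gives 27, at m = 3 or m = 4. Attrition then reproduces: 27/(1 − 0.25) = 36.

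**Step 3: direction of the ICC.** Required n per arm, from 32 × factor:

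| Quantity | ICC 0.60 | ICC 0.75 |
|---|---|---|
| Average, m = 3 | 23.5 | 26.7 |
| Before-after change | 25.6 | 16.0 |
| Change in cue-induced change | 51.2 | 32.0 |

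The requirement rises with the ICC for the average and falls for both changes.

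**Step 4: power for the change contrasts.** Two-sided t-test, difference 8.5:

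| Reading of 12.2 and contrast | SD of contrast | 27 per arm | 36 per arm |
|---|---|---|---|
| (a) SD of the score at each visit; before-after change | 12.2√0.5 = 8.6 (ICC 0.75); 12.2√0.8 = 10.9 (ICC 0.60) | 94%; 80% | 98%; 90% |
| (b) Already the SD of the analysed before-after change | 12.2, no ICC discount | 71% | 83% |
| (c) SD of one raw score; change in cue-induced change, four scores equally correlated | 12.2√1.0 = 12.2 (ICC 0.75); 12.2√1.6 = 15.4 (ICC 0.60) | 71%; 51% | 83%; 63% |

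Reading (a) covers one MCQ score. It also covers the per-visit cue-induced change, if 12.2 is the SD of that quantity and the ICC is between visits.

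**The case against.** An average may have been intended. The schedule lists MCQ at baseline, the final rTMS visit, two weeks and four weeks: three post-baseline assessments or four in all, the two values of m that give 27. The protocol's Statistical Analysis plans group comparisons over all planned time points, and attrition is counted to the four-week visit. If 12.2 is the SD at each visit, 27 follows and 0.75 is the cautious value, as the text claims. This reading is possible but less well supported. Aim 1 compares after the last session with before the first, the rTMS Sessions section places the full cue paradigm at those two points, and the sizing paragraph itself speaks of measuring before and after the course.

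A reader might infer that the ICC was used to cut the size from 32 to 27, contradicting the remark about a reduced effective sample size. That takes 32 as per arm. The text calls it a total, and read literally the size rises from 16 to 27 per arm. The arithmetic favours the per-arm reading, but it remains an inference.

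A reader might also infer that the trial is underpowered, at 51-71%. The documents do not establish that. The range needs 12.2 to be a raw-score SD and all four scores to be equally correlated. If correlations across sessions are equal, the ICC in 4(1 − ICC) is the correlation between pre-cue and post-cue scores within a session, which may exceed a correlation across weeks. At an assumed 0.80, the SD is 12.2√0.8 = 10.9 and power with 27 per arm is 80%. The SAP models total MCQ-SF by treatment and time, closer to reading (a), which keeps 80-94%. It uses the full ITT sample of 72, and the protocol plans last observation carried forward, so the 36-per-arm figures are also relevant.

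What stands of the objection is that the size of any shortfall is unsettled. It does not make 27 a derivation for a change, or 0.75 the cautious ICC for one.

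**Conclusion.** The Aim 1 derivation does not fit the Aim 1 hypothesis. Its 27 per group agrees with the variance of an average of three or four scores and with none of the change formulas tried. For a change, calling 0.75 conservative points the wrong way: moving from 0.75 to 0.60 raises the required n by 60%, from 16.0 to 25.6 or from 32.0 to 51.2 per arm. The total of 32 is also inconsistent with 80% power at one observation each.

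The averaging formula is inferred from the result, since none is named.

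This does not show that the trial was too small. With 27 per arm, power is 80-94% under reading (a), 71% under (b), and 51-71% under (c) with its assumptions. The documents do not say which reading holds, so adequate power is neither demonstrated nor refuted.

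**What to change.** Rewrite the Aim 1 paragraph to:

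- say what 12.2 and 8.5 refer to (one MCQ score, the cue-induced change at a visit, or the before-after change);
- name the primary contrast;
- correct the total of 32 to 32 per arm, or state the design under which 32 in total holds;
- replace the 27-per-group derivation with power for the named contrast at ICC 0.60 and 0.75, for 27 and 36 per arm, treating 0.60 as the conservative value;
- drop the conservative label for 0.75.

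Quote 51-71% only if the contrast is the change in cue-induced change, with the raw-score SD and equal-correlation assumptions beside it.

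The cost is one rewritten paragraph and possibly a less favourable stated power. No extra patients are needed.

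### The Aim 1 power base gives 80% power to 32 participants in total; that power belongs to about 32 per group, so the base is most likely mislabelled, with no shortfall shown in N=72

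*Combined protocol and SAP*

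**What the plan says.** The calculation is in the combined protocol and SAP, section D, Sample Size Justification, Aim 1 part. It sets out to detect a "craving score difference between the two treatment groups of 8.5" MCQ points "with a standard deviation of ≈ 12.2", which it rounds to d=0.7, and it takes an ICC of 0.75. It notes that craving is measured before and after the treatment course.

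It then takes three steps:

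- **Base, assuming independent observations.** "a total sample size of 32 participants equally allocated to each treatment assignments will provide 80% power" for d=0.7 at a 5% type 1 error rate.
- **ICC step.** The reason given is that "the effective sample size in a repeated measures data setting is reduced when assuming an ICC of 0.75"; from this the plan arrives at 27 per group.
- **Attrition step.** Allowing for up to 25% attrition, 36 per group and 72 in total.

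The base is given as a total and the next two steps per group. The Aim 1 part does not say how many observations per participant are counted, names no formula and does not give the sidedness of the test. The SAP is explicit on the last point for the analysis: "a level of $\alpha = 0.05$ was used (two-tailed"). The SAP also names craving as the one outcome for which the trial was powered in advance.

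**The concern.** A reader who checks the base sentence with an ordinary two-group power formula finds about half the power claimed. The sentence supports the one outcome that the SAP treats as powered, so it should be possible to reproduce it.

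The change of unit also hides which way the ICC step moves the requirement. Read as printed, the number per group rises from 16 to 27. Read as 32 per group, it falls from 32 to 27. These are different calculations, and the text does not say which one was done. Anyone who took the base figure over for a comparison with one outcome score per participant would have under 50% power at d=0.7.

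**Working it through.** **Inputs** (Sample Size Justification, Aim 1): difference 8.5; SD 12.2; d = 8.5/12.2 = 0.697, stated as 0.7; alpha 5%; ICC 0.75; attrition 25%. The test is taken as two-sided, from the SAP.

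**1. The base sentence, one observation per participant.** For n per arm, normal-approximation power is Φ(d√(n/2) − 1.960).

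- n=16 (32 in total): 0.7 × √8 = 1.980; Φ(0.020) = 50.8%.
- n=32 (64 in total): 0.7 × √16 = 2.800; Φ(0.840) = 80.0%.

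The two-sided t-test column uses the noncentral t distribution.

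| Per arm | Normal, d=0.70 | t-test, d=0.70 | t-test, d=0.697 |
|---|---|---|---|
| 16 | 50.8% | 48.3% | 47.9% |
| 27 | 73.0% | 71.4% | 71.0% |
| 32 | 80.0% | 78.7% | 78.3% |
| 36 | 84.4% | 83.4% | 83.0% |

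A one-sided 5% test does not rescue 16 per arm (61.4% by t-test, 63.1% by normal approximation). In the other direction, the number per group for 80% power is 2 × (1.960 + 0.842)²/0.7² = 32.04. The printed 32 is therefore the usual normal-approximation figure per group.

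**2. Where the 27 comes from.** With k equally correlated observations per participant, each carrying the same treatment difference, the number per group is 32.04 × [1 + (k−1) × 0.75]/k. If the observations were independent, it would be 32.04/k.

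| k | Per group if independent | Per group at ICC 0.75 |
|---|---|---|
| 1 | 32.04 | 32.04 |
| 2 | 16.02 | 28.03 |
| 3 | 10.68 | 26.70 |
| 4 | 8.01 | 26.03 |

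A total of 32 (16 per group) under independence requires k=2, but k=2 then gives 28. The stated 27 follows, rounding up, from k=3 or k=4. The schedule of assessments lists the MCQ at four visits, three of them after baseline. No single k in this formula gives both 32 in total and 27 per group. A base of 32 per group with three or four measures does give 27. This formula is my assumption, because the protocol names none. A one-sided t-test at d=0.697 with one observation each also needs 27 per group, which is a further reason to state the method.

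**3. Attrition.** 27/(1 − 0.25) = 36 per group, 72 in total. This reproduces the plan exactly and does not depend on how the 32 is labelled.

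**4. Power of the final design.** On a single post-treatment comparison (t-test, d=0.70), power is 83% with 36 per arm and 71% with 27 completers per arm. For a pre-to-post change score, assume that SD 12.2 applies at each occasion and that the correlation is 0.75. The change then has SD 12.2 × √(2 × 0.25) = 8.63, the effect becomes 0.7/√0.5 = 0.99, and 27 per arm give about 95%.

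**The case against.** The strongest defence is that the base sentence is conditional on independent observations and sits in a paragraph about repeated measures. If observations are the unit, 32 participants with two scores each give 64 observations, or 32 per arm, and the stated 80% is reproduced (80.0% normal, 78.7% t-test). The direction of the text also fits: 16 per group rises because correlation costs information.

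This keeps the reading possible, but it does not clear the sentence. The text counts participants and gives no number of observations. The ICC step on this reading gives 28, one more per group than stated. The reading also needs the pre-treatment score to carry the treatment effect. Section A states the Aim 1 hypothesis as craving after the final session compared with craving before the first, and randomisation leaves no expected difference at baseline. If the two scores were independent and only the later one carried the effect, a change score would have SD 12.2 × √2, an effect of 0.7/√2 = 0.495, and 27% power with 16 per arm (t-test, SD 12.2 assumed at each occasion).

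A change score at correlation 0.75 does bring 16 per arm to 80% by normal approximation (77% by t-test). But it uses the correlation that the base sentence sets aside, and no later increase to 27 for the ICC would then be needed.

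Two further points for the plan stand in full. The design is 36 per arm, not 16, and none of the power figures for it is near 48%. And the choice between 32 and 34 per group (the two-sided t-test needs 34) is only a choice of approximation, not an error.

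**Conclusion.** The base sentence is wrong on its plain reading: 32 participants in total give about 48% power at d=0.7, not 80%. The likeliest explanation is a per-group number labelled as a total. This rests on a two-sided 5% test and one observation per participant. The alternative, two independent observations each, is neither stated nor consistent with the Aim 1 hypothesis, and it misses the stated 27 by one per group.

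A reader might infer that 27 per group and N=72 inherit an error of a factor of two, or that the trial has half the power claimed. The documents do not support this. With 32 read as per group, 27 follows for three or four measures, and 36 per group follows from 27 exactly. What remains open is the power of the final design, because it depends on the comparison: 71% on a single post-treatment score with 27 completers per arm, about 95% on a change score if SD 12.2 holds at each occasion and the correlation is 0.75.

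**What to change.** Rewrite the Aim 1 paragraph so that each step can be reproduced:

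- Restate the base, for example: *With one observation per participant, 32 per group (64 in total) give 80% power for d=0.7 at two-sided 5% by normal approximation (78.7% by t-test).* If repeated observations were counted instead, say so and state which ones.
- Use per-group units in every step.
- State the number of observations per participant, the design-effect formula and the sidedness that lead to 27.
- Restate the power of 36 randomised and 27 completing per group for the Aim 1 comparison as planned, with the SD and correlation assumed.

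The cost is one paragraph of wording. No extra patients are needed. The stated power may come out slightly below 80% for the base if the t-test figure is used, and below 80% for 27 completers if the planned comparison is a single post-treatment score.

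### The 80% power stated for abstinence assumes no attrition and a mid-range placebo rate; with the plan's own 25% attrition it is about 58–77%

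*Combined protocol and SAP*

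**What the plan says.** The power statement is the last part of the Sample Size Justification in the combined protocol and SAP. It reports that the group's earlier trials showed "varying placebo abstinence rates (defined as ≤ 50 ng/ml THCCOOH UCT) at the end of study (EOS) treatment (5-15" per cent). It then takes a gain of 30 over placebo and puts the claim this way: "most conservative conditions, at a 10% placebo abstinence rate, a randomized sample size of 36 participants in each treatment group will provide 80% power". The type 1 error is given as 5%. No test is named there. The Statistical Analysis section plans logistic regression for the abstinence proportion at the four-week follow-up.

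Earlier in the same Sample Size Justification, the Aim 1 calculation provides for losses between randomisation and the 4-week follow-up visit: "Assuming an attrition rate of up to 25" per cent, the 27 needed per group are raised to 36. The abstinence statement does not mention attrition.

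Two missing-data rules appear elsewhere. The protocol's paragraph on relapse and drop-out carries the last observation forward for every outcome. The 2023 SAP, for weeks of abstinence (Aim-2a), says "We conservatively imputed missing values as non-abstinent, thereby including the total ITT sample".

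**The concern.** A figure presented as a worst case should use the least favourable value of each input the plan gives. Here the placebo rate is the mid-point of the quoted range, and the calculation uses every randomised participant, although the section has just said that up to a quarter may be lost by the visit at which this endpoint is assessed. The statement matters because the protocol rests on it a claim that the trial still has power for a large effect on abstinence. If true power is well below 80%, a null result says less against a large effect than a reader of that sentence would suppose. The trial's stated purpose for this aim is to inform the size of a later study.

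**Working it through.** **Inputs.** Placebo rate 10%, quoted range 5–15%, gain 30, 36 per arm, type 1 error 5% and attrition up to 25% all come from the Sample Size Justification. Two-sidedness is not stated in the abstinence sentence. It is taken from the SAP ("a level of $\alpha = 0.05$ was used (two-tailed") and agrees with the two-tailed level given for Aim 2. The gain is read as absolute: a relative 30% (10% versus 13%) would give only about 2–8% power, which cannot be what was meant.

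**Method.** Exact power is the sum, over all pairs (a, b) of abstinent counts, of Bin(a; n, p₁) × Bin(b; n, p₂) for those tables where the test gives p ≤ 0.05. The logistic likelihood-ratio and Wald tests are unadjusted; for Wald, tables with a zero cell count as not significant.

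**Reproducing 80%.** At n = 36, 10% versus 40%, two-sided Fisher gives 80.0%, as does the continuity-corrected chi-square. Other two-sided methods differ: uncorrected chi-square 86.4%, logistic likelihood ratio 87.9%, logistic Wald 83.9%, continuity-corrected normal formula 77.5%.

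**Attrition.** 36 × (1 − 0.25) = 27 evaluable per arm.

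| n per arm | Rates | Fisher | Uncorrected chi-square | Logistic LR | Logistic Wald |
|---|---|---|---|---|---|
| 36 | 5% v 35% | 88% | 93% | 94% | 76% |
| 36 | 10% v 40% | 80% | 86% | 88% | 84% |
| 36 | 15% v 45% | 74% | 82% | 83% | 81% |
| 27 | 5% v 35% | 72% | 86% | 86% | 57% |
| 27 | 10% v 40% | 63% | 77% | 77% | 68% |
| 27 | 15% v 45% | 58% | 71% | 72% | 66% |

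**Hand check.** The pooled normal formula is power = Φ{[d − 1.96√(2p̄(1−p̄)/n)] / √[(p₁(1−p₁)+p₂(1−p₂))/n]}, with d = 0.30.
- n = 36, 10% v 40%: (0.30 − 1.96 × 0.1021)/0.0957 = 1.04, power 85.2%.
- n = 36, 15% v 45%: (0.30 − 1.96 × 0.1080)/0.1021 = 0.87, power 80.7%.
- n = 27, 10% v 40%: (0.30 − 1.96 × 0.1179)/0.1106 = 0.62, power 73.4%.
- n = 27, 15% v 45%: (0.30 − 1.96 × 0.1247)/0.1179 = 0.47, power 68.1%.

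This formula needs 32 per arm for 80% at 10% versus 40%, so even on this more favourable basis the claim survives a loss of only 4 of 36 (11%).

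**Placebo rate.** From 10% to 15%, power falls under every test. From 5% to 10% it also falls under Fisher, chi-square and likelihood ratio. Wald is the exception at 5%, because zero cells make it fail. Ten per cent is therefore not the unfavourable end of the range.

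**The case against.** The strongest reply is that the printed figure is arithmetically right for its stated inputs and that the rest is sensitivity analysis on a minor aim. The protocol says the sample is not designed to settle this question. The SAP says that nothing but craving was powered in advance, and it replaces the binary logistic analysis with weeks of abstinence and days of use. All of that stands and limits the harm. It does not cure the statement, because the protocol follows its disclaimer with a claim of power for a large effect, supported by the 80%.

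A second reply is that the 25% belongs to Aim 1 and that the last-observation rule keeps all 36 in the analysis. But the allowance is defined up to the 4-week visit, where abstinence is assessed. The endpoint also needs a four-week to two-week urine ratio, and the plan does not say what would be carried forward for someone with no four-week sample. If 10% and 40% were already rates among all randomised, with dropouts counted as non-abstinent, attrition would be absorbed; the documents do not say so.

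Four stronger readings are tempting and are not supported:

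- *The 15% placebo rate alone breaks the claim.* It does so under Fisher (74%), but not under the planned logistic regression or an uncorrected chi-square (81–83%).
- *With attrition, no test reaches 80% anywhere in the range.* At 5% versus 35% with 27 per arm, chi-square and likelihood ratio give 86%.
- *Power may be as low as 54%.* That figure counts 25% as non-abstinent among 36 (0.75 × 15% = 11.25%, 0.75 × 45% = 33.75%; Fisher 54%). It borrows a rule the SAP states for a different endpoint, and may deduct attrition twice.
- *The 50 ng/ml definition behind the placebo rates invalidates the power.* The definition does differ from the endpoint's, but the documents give no basis for a direction or size of effect.

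**Conclusion.** The concern holds in this form. The 80% rests on a mid-range placebo rate and all 36 per arm being analysed, and it is matched exactly only by a two-sided Fisher test or its continuity-corrected equivalent. With the plan's own upper attrition figure, power is about 63–77% at 10% versus 40% and about 58–72% at 15% versus 45%. A true 30-point effect would then be missed roughly 23–42% of the time (100 − 77 to 100 − 58), against the stated 20%. Attrition does the damage; the 15% rate alone does not, under the planned analysis.

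This assumes two-sided testing, an absolute 30-point gain, equal attrition in both arms unrelated to outcome, and dropouts left out of the comparison. The allowance is not pessimistic in hindsight: the SAP's completer sample of 51 of 72 means 21/72 = 29% had no follow-up data. Because the aim is exploratory and did not set the sample size, the error affects how a null result is read and leaves the design unchanged.

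**What to change.** Rewrite the one sentence in the Sample Size Justification, and carry the correction into any report that quotes it:

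- remove the claim that 10% is the most conservative condition;
- name the test, and say that 80% is for two-sided Fisher at 10% versus 40% with all 36 per arm analysed;
- add that with 25% attrition (27 per arm) power is about 58–77% across placebo rates of 10–15%, depending on the test;
- if dropouts are to be counted as non-abstinent, state whether the assumed 10% and 40% already include them.

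The cost is one sentence and a less favourable figure. No participants, data or analyses change.
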